4 STUDY DESIGN

- This is a cross-sectional study designed to identify the proportion of the study population with an oral high-risk HPV infection that will be offered enrollment into a longitudinal study with a 6-month follow up visit; the study will consist of a single baseline visit for the overwhelming majority (approximately 97.5%) of participating patients.
- The study population will consist of a target of 1,000 men and women age 30-69 years old. In order to avoid a situation where enrollment is cut off in the middle of a business day, up to 1,200 enrollments may be allowed. Enrollment will be halted within approximately 48 hours of reaching the target of 1,000 patients.
- Patients will be recruited during routine clinical visits with participating National Dental PBRN dental practitioners. Approximately, five practice locations will be recruited from each of the six National Dental PBRN regions: Northeast, South Atlantic, South Central, Midwest, Southwest, and Western regions. The approximately 30 total practice locations will be strategically selected to represent diverse dental practice types. Approximately 40 practitioners will be recruited among the approximately 30 practice locations.
- Each participating practitioner will be expected to enroll approximately 25-50 patients, total. For example, at a rate of one patient enrolled per day, enrollment may be complete in approximately five weeks.
- Enrolled patients will participate using a tablet computer, which will explain the study, assess patient eligibility, obtain electronic consent (Appendix A), administer the oral HPV risk factor survey (Appendix C) and determine patient selection for oral rinse collection.
- Based on the oral HPV risk factor survey responses, the top three deciles of risk (about 300 patients) and a random selection of those in the lower deciles will be selected for oral rinse collection. An oral rinse sample will be obtained by means of a 30-second rinse and gargle with Scope™ mouthwash (or saline), expectorated into a sterile specimen collection cup, sealed and stored at 4°C. Specimens will be shipped by practice staff approximately weekly or twice a week to a central laboratory for HPV detection.
- The results of the oral rinse test for high-risk HPV will be communicated to practitioners through the study's secure web application. A 3-tiered approach will be implemented to inform patients of test results:
 - (1) The dentist will be the first to provide the test result;

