11.2 Sample Size Considerations

The sample size for this pilot study is based upon a dichotomous outcome in which participating patients are categorized as low-risk versus high-risk for oral high-risk HPV infection. Based upon our risk model derived from 5,500 individuals who are representative of the US population (NHANES), we expect 30% of the study population to be categorized as high-risk. A two-sided test of proportions with a type 1 error of 0.05 indicates that a pilot study with 1,000 individuals will have 90% power to detect a 5% or greater difference in the proportion of the study population that is categorized as high-risk. The ability to enroll a sample size of 1,000 will also provide assurance that a study with a large sample size is feasible in the National Dental PBRN.

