To accomplish secondary objective (2) the distribution of the demographic and behavioral variables in the study population will be compared to the weighted distribution of the same factors in the US population per NHANES. In this analysis, the distribution of the populations into deciles of risk will be represented in an $n \times k$ table where n represents the two populations and k the deciles of risk. The distribution will be compared by chi square test with nine degrees of freedom. The distribution of each variable in the two populations will also be compared in univariate analysis. Successful completion of this pilot will therefore: (1) assess patient acceptability of the procedures; (2) provide training to study personnel and assess the feasibility of incorporating the study procedures into clinical practice; and (3) inform the point estimates and models used for sample size determination for a future larger study to ensure that the estimate of 60,000 screened individuals is appropriate.

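### The 90% power in 11.2 and the nine-df chi-square in 11.3 assume independent patients, although about 25 are recruited per practitioner; no ICC or design effect is stated

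*Protocol*

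**What the plan says.** Section 11.2 bases the sample size on "A two-sided test of proportions with a type 1 error of 0.05". The reference comes from the NHANES risk model: "we expect 30% of the study population to be categorized as high-risk". The conclusion is that "a pilot study with 1,000 individuals will have 90% power to detect a 5% or greater difference in the proportion of the study population" placed in the high-risk class.

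Section 11.3 tabulates 95% bounds around 8.43% for 100 to 500 tested patients. For secondary objective (2) it sets the study sample against the weighted NHANES population in a table of two populations by ten risk deciles: "The distribution will be compared by chi square test with nine degrees of freedom".

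Section 4 describes the recruitment. "Approximately 40 practitioners will be recruited among the approximately 30 practice locations", and "Each participating practitioner will be expected to enroll approximately 25-50 patients, total". Also, "The approximately 30 total practice locations will be strategically selected to represent diverse dental practice types". Section 5.3.3.1 adds that patients are a convenience sample within practices. Neither 11.2 nor 11.3 mentions clustering, an ICC or a design effect.

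**The concern.** Risk class is built from age, gender, number of sexual partners and smoking (section 2.2). These can be expected to differ between an inner-city public clinic and a rural private practice, and section 5.3.1 sets recruitment targets across just such categories. If patients of one practitioner resemble each other, 1,000 patients carry less information than 1,000 independent ones.

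Two things would follow. The power in 11.2 would be lower than stated. The chi-square in 11.3, if left unadjusted, would also reject too often. Hypothesis (3) in section 11.1 is that the risk-factor distribution resembles that of the US population, so noise between practices could be read as real dissimilarity. Section 11.3 also says that the pilot will inform the models behind the planned 60,000-person study, so the omission could carry forward.

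**Working it through.** **Inputs.** From 11.2: N = 1,000, two-sided alpha 0.05, reference 30%, NHANES sample 5,500. The 5% difference is read as 5 percentage points, so the alternatives are 25% and 35%; a relative 5% (1.5 points) would give only about 18% power. From section 4: 1,000/40 = 25 patients per practitioner, or 1,000/30 = 33 per practice. The ICC is not in the document; 0.01, 0.02 and 0.05 are assumptions.

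**Step 1: reproduce the 90% with independent patients.**

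- *Fixed 30%.* Power = Φ[(0.05 − 1.96·√(0.30·0.70/1,000)) / √(p₁(1−p₁)/1,000)].
  - p₁ = 35%: (0.05 − 1.96·0.01449)/0.01508, giving 92.4% (exact binomial 91.3%).
  - p₁ = 25%: (0.05 − 1.96·0.01449)/0.01369, giving 94.3% (exact binomial 94.1%).
- *NHANES as a second sample, 1,000 vs 5,500.*
  - p₁ = 25%: pooled SE 0.01564, SE under the alternative 0.01502, z = (0.05 − 1.96·0.01564)/0.01502 = 1.288, giving 90.1%.
  - p₁ = 35%: 87.7%.

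The stated figure is therefore recovered to within a few points by either reading, always with a design effect of 1. The closest match is 1,000 vs 5,500 at 25% vs 30%.

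**Step 2: slack before 90% is lost.** Design effect DE = 1 + (m − 1)·ICC, with m = 25.

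- Fixed 30%, 35% alternative: 911 independent patients are needed. DE may reach 1,000/911 = 1.097, so ICC = 0.097/24 = 0.004.
- Fixed 30%, 25% alternative: 845 are needed. DE may reach 1.184, so ICC = 0.184/24 = 0.008.
- Two-sample, 25% alternative: the limit is an ICC of about 0.0002. For 35%, power is below 90% from the start.

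An ICC of 0.004 means that true high-risk proportions vary between practitioners with an SD of √(0.004·0.21) = 2.9 points around 30%.

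**Step 3: power with clustering (m = 25, effective N = 1,000/DE).**

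| Assumed ICC | DE | Effective N | Fixed 30%: 25% / 35% | Vs 5,500: 25% / 35% |
|---|---|---|---|---|
| 0.01 | 1.24 | 806 | 88.6% / 86.3% | 84.0% / 81.3% |
| 0.02 | 1.48 | 676 | 82.3% / 80.0% | 77.8% / 75.2% |
| 0.05 | 2.20 | 455 | 65.1% / 63.8% | 61.7% / 60.2% |

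With practice as the cluster (33 each), an ICC of 0.02 gives DE 1.65 and 78.0% / 75.8% against a fixed 30%. At DE 1.48 and a fixed 30%, 90% power corresponds to an upward difference of about 5.8 points.

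**Step 4: size of an unadjusted chi-square.** To first order, size = P(χ²₉ > 16.92/s), with one design effect applied to all deciles.

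- *NHANES fixed, s = DE:* 13.6%, 24.7% and 56.6% at ICC 0.01, 0.02 and 0.05.
- *NHANES as 5,500 independent subjects:* s = (DE/1,000 + 1/5,500)/(1/1,000 + 1/5,500) = 1.20, 1.41 and 2.02, giving 12.0%, 21.2% and 49.5%.

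**Step 5: confidence interval table.** All five rows equal 8.43% ± 1.96·√(p(1−p)/n) to two decimals, so the design effect is again 1. At n = 300 there are about 300/40 = 7.5 tested patients per practitioner, and DE = 1 + 6.5·ICC. The printed 5.29-11.57% becomes 5.19-11.67%, 5.09-11.77% and 4.81-12.05% at ICC 0.01, 0.02 and 0.05, a shift of about 0.1 to 0.5 points per bound.

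**The case against.** The strongest reply is that nothing is miscalculated: the power and every table row reproduce. The opening of section 11 refers further detail on power to an SAP that is not shown, and that SAP may supply a cluster correction. Section 11.3 excludes none, and it already speaks of a weighted NHANES distribution. The practice quotas in section 5.3.1 act somewhat like stratification and could lower the variance.

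Much of this limits the point. A reader might infer that the power is simply not delivered and that the chi-square does over-reject. The document gives no ICC, so both hold only if the ICC exceeds the small thresholds above (for power) or is positive and unadjusted (for the test). A reader might also infer that the 90% arises only against a known 30%. It does not, because 1,000 vs 5,500 at 25% gives 90.1%, so the authors may already have allowed for NHANES sampling error. Nor is the confidence interval table materially too narrow: 0.5 points at most over this ICC range, beside a half-width of 3.1 points at n = 300.

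The reply does not rescue the stated figures. The protocol itself prints an independence-only power and names a test with no adjustment. Weighting NHANES does not account for clustering on the study side. The quotas would have to remove nearly all between-practitioner variation to keep the ICC within the slack.

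**Conclusion.** The point holds conditionally. The 90% power rests on an unstated assumption of independent patients that the recruitment design makes doubtful, with little room for error: an ICC of about 0.004 to 0.008 against a fixed 30%, and essentially none if NHANES is treated as a sample. Over assumed ICCs of 0.01 to 0.05, power is roughly 60-89%, and an unadjusted chi-square would have a true size of roughly 12-57%.

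These figures assume equal clusters of 25; unequal clusters of 25-50 would raise the design effect. The chi-square sizes are approximations. The NHANES survey design effect is not included in the two-sample figures.

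Severity is below must-fix. The study is a pilot whose primary objective is estimation, and the chi-square serves secondary objective (2).

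**What to change.** **Section 11.2.** State an assumed ICC range and design effect, and give the power across it. For example, against a fixed 30% with 25 patients per practitioner and ICC 0.02, power is about 80% for an upward difference of 5 points, or 90% for about 5.8 points. Say whether the 30% is treated as fixed or as estimated from NHANES.

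**Section 11.3.** Replace the plain chi-square by a Rao-Scott (design-based) test, with practice as the cluster for the study sample and the NHANES weights, strata and primary sampling units for the reference. Use practice-clustered variances for the study proportions and their intervals.

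**Cost.** Wording and routine survey procedures, a less favourable stated power and slightly wider intervals. No extra patients are needed.

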11.3 Final Analysis Plan

To accomplish the primary objective, our outcomes of interest will be the number of individuals determined to be in the top three deciles of risk based on our model (i.e., those selected for oral sample collection based on risk) as well as the proportion of those individuals with an oral high-risk HPV infection. Based upon our model in NHANES, we would expect that 30% of the participating population would be selected for specimen collection and that the resulting population would have an oral high-risk prevalence of 8.43% (95%CI 6.68% to 10.14%). The number of individuals selected as high-risk will be informative with regard to the distribution of

risk factors in the study population, and the proportion positive will be informative with regard to the β -estimates for our risk model.

Shown in the table below are the upper and lower bounds of the 95% CI for the proportion positive for oral high-risk HPV infection, assuming a range of 10-50% of the study population is categorized as high-risk based on our model. A proportion of the study population with oral high-risk infection that falls within the confidence bounds in the table below, given the sample size, will indicate that the β -estimates in our NHANES model are reasonable estimates of risk to the study population.

Sample size	Proportion	95% Confidence Interval	
		Lower Bound	Upper Bound
100	8.43%	2.98%	13.88%
200	8.43%	4.58%	12.28%
300	8.43%	5.29%	11.57%
400	8.43%	5.71%	11.15%
500	8.43%	5.99%	10.87%

To accomplish secondary objectives (1) and (3) a brief Provider Survey (Appendix P) will be administered via tablet computer/web-application to providers at each participating practice to assess acceptability of each procedure and willingness to participate in a future larger study. Results will be reported as summary statistics.

Descriptive statistics for secondary objective (3) include the proportion of individuals with high-risk oral HPV infection who:

- (1) Enroll in the follow-up study;
- (2) Attend a 6-month follow-up;
- (3) Provide blood serum sample; and
- (4) Provide second oral rinse.

To accomplish secondary objective (2) the distribution of the demographic and behavioral variables in the study population will be compared to the weighted distribution of the same factors in the US population per NHANES. In this analysis, the distribution of the populations into deciles of risk will be represented in an $n \times k$ table where n represents the two populations and k the deciles of risk. The distribution will be compared by chi square test with nine degrees of freedom. The distribution of each variable in the two populations will also be compared in univariate analysis. Successful completion of this pilot will therefore: (1) assess patient acceptability of the procedures; (2) provide training to study personnel and assess the feasibility of incorporating the study procedures into clinical practice; and (3) inform the point estimates and models used for sample size determination for a future larger study to ensure that the estimate of 60,000 screened individuals is appropriate.

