- Précis:** A target of 1,000 men and women aged 30-69 years will be enrolled over a 6-month period, with up to 1,200 enrollments allowed to avoid cutting off enrollment in the middle of a business day. Approximately thirty practice locations will be recruited from the 6 National Dental PBRN regions (approximately 5 practice locations per region). Approximately 40 practitioners will be recruited among the approximately 30 practice locations. Participating patients will be recruited during routine clinical visits with participating National Dental PBRN practitioners. Each practitioner will recruit approximately 25-50 patients. Patients will be provided a tablet computer on which the study will be explained, electronic consent will be obtained, patient eligibility will be assessed, an oral HPV risk factor survey will be administered, and patient selection for oral rinse collection will be determined. Based on survey responses, the top three deciles of risk (~300) and a random selection of 1 in 12 of those in the lower deciles (~59) will be selected for oral rinse collection (~359 total). An oral rinse sample will be obtained by means of a 30 second rinse and gargle with Scope™ mouthwash (or saline), expectorated into a sterile specimen collection cup, sealed and stored at 4°C. Specimens will be shipped by practice staff approximately weekly or twice a week to a central laboratory for human papillomavirus (HPV) detection. HPV results will be communicated to the dental practitioner through the study's secure web application. Patients with a high-risk oral HPV infection (anticipated to be ~25 individuals) will be offered enrollment into a prospective study inclusive of a blood draw, an oral cancer examination, and a 6-month follow-up dental visit (window: 5-9 months) with a repeat oral rinse and an electronic oral cancer risk factor survey. Patients will be compensated with a gift card for each major study procedure.
- Objectives:** The primary objective of this study is to estimate the proportion of the study population with an oral high-risk HPV infection.
- The secondary objectives of this study are to:
- (1) Evaluate the feasibility and acceptability of baseline study procedures performed by participating patients and staff;
 - (2) Measure the distribution of demographic and behavioral

characteristics associated with oral HPV infection;

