3 OBJECTIVES

3.1 Study Objectives

The primary objective of this study is to estimate the proportion of the study population with an oral high-risk HPV infection.

The secondary objectives of this study are to:

- (1) Evaluate the feasibility and acceptability of baseline study procedures performed by participating patients and staff;
- (2) Measure the distribution of demographic and behavioral characteristics associated with oral HPV infection; and
- (3) Determine compliance with and feasibility of procedures performed at a 6-month follow-up visit (window: 5-9 months), including blood draw, second oral rinse specimen collection, oral cancer screening examination, and completion of an oral cancer risk factor survey (Appendix J).

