3.2 Study Outcome Measures

The primary study outcome measure is the proportion of the study population with an oral high-risk HPV infection, which will be assessed through laboratory testing of the oral rinse specimen, recorded on a laboratory testing electronic Case Report Form (eCRF).

Secondary study outcome measures corresponding to the secondary objectives noted above will include:

- (1) The feasibility and acceptability of baseline study procedures performed by participating patient and dental office staff as assessed through:
 - a. Patients:
 - i. Electronic study summary (Appendix A): proportion of patients who agree to learn more about the study; proportion of patients who screen eligible to participate; proportion of patients who agree to the electronic consent.
 - ii. Oral HPV risk factor survey (Appendix C): acceptability of questions about risk factors ascertained in the survey.
 - b. Dental office staff:
 - i. Practitioner acceptability: Practitioners approached to participate in the study, those who agree or decline participation during the consent process, and practitioners who complete study-specific training.
 - ii. Feasibility (protocol education/training; patient recruitment; patient consent; answering questions; collecting, storing, and shipping oral rinses; distributing gift cards; providing test results).

-
- iii. Provider survey (Appendix P): ascertains acceptability (acceptability of extra time required for study procedures; comfort with study procedures; interest in participating in a future study) among practice staff.
- (2) The distribution of demographic and behavioral characteristics associated with oral HPV infection as assessed by the oral HPV risk factor survey (Appendix C) (gender; age; race/ethnicity; marital status; education; cigarette smoking; lifetime number of sexual partners) stratified by oral HPV status (laboratory testing eCRF).
- (3) The compliance with and feasibility of procedures done at the 6-month follow up visit performed by participating patients and dental office staff as assessed through:
- a. Patients:
 - i. eCRFs completed by the Regional Coordinator (RC), and will include a proportion of individuals with oral high-risk infection who: (a) enroll in the prospective study; (b) attend a 6-month follow-up; (c) undergo phlebotomy; (d) undergo ENT exam; and (e) complete the Oral Cancer Risk Factor Survey (Appendix J).

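### Section 11.3 answers the primary objective with positivity in the top three risk deciles (8.43% expected), not with the study-population proportion that sections 3.1 and 3.2 define

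*Protocol*

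**What the plan says.** Section 3.1 of the protocol states: "The primary objective of this study is to estimate the proportion of the study population with an oral high-risk HPV infection". Section 3.2 repeats it as the outcome: "The primary study outcome measure is the proportion of the study population with an oral high-risk HPV infection". Section 4 says who that population is: "The study population will consist of a target of 1,000 men and women age 30-69 years old".

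Rinses are not taken from everyone. Under the Précis in the Protocol Summary, the top three risk deciles (about 300 patients) are selected, and "a random selection of 1 in 12 of those in the lower deciles (~59) will be selected for oral rinse collection", about 359 rinses in all. Section 4 describes the same two-part selection without the 1-in-12 fraction.

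Section 11.3 sets out how the primary objective will be met: "our outcomes of interest will be the number of individuals determined to be in the top three deciles of risk based on our model", "as well as the proportion of those individuals with an oral high-risk HPV infection". It expects 30% of participants to be selected for specimen collection and a prevalence of 8.43% among them. It then tabulates 95% limits around 8.43% for 100 to 500 patients. The risk model is to be judged reasonable if the study-population proportion lies within those limits.

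Section 11.2 says the sample size "is based upon a dichotomous outcome in which participating patients are categorized as low-risk versus high-risk for oral high-risk HPV infection".

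**The concern.** The objective concerns all enrolled patients. The analysis said to accomplish it concerns the 30% with the highest predicted risk. Neither quantity named in section 11.3, the number classified high-risk or the positivity among them, is the study-population proportion.

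The rinses that would make that proportion estimable are planned and collected, but the primary-analysis text in section 11.3 does not use them. It gives 30% as the share selected for specimen collection, whereas section 6.2.1 gives about 35.9%; the difference is the lower-decile sample. No weighting or combination of the two strata is described in the protocol.

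The decision rule has the same fault: it names a study-population proportion but compares it with limits built for the top three deciles. Followed literally, the study either reports the prevalence of a risk-enriched subgroup as its primary result, or compares a correct population figure with the wrong limits and doubts a model that fits.

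**Working it through.** **Inputs**
- Share in the top three deciles: 30%, about 300 of 1,000 (sections 11.2 and 11.3, Précis).
- Expected prevalence in that stratum: 8.43% (section 11.3).
- Lower-decile rinses: about 59, from about 700 patients (Précis).
- Expected positives among everyone tested: about 25, or 2.5% of patients (Précis, section 6.2.1).
- Lower-decile prevalence, pL: not given. It is assumed below, starting at 0%.

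**1. Reproduce the table in section 11.3.** The limits are p ± 1.96 × √(p(1 − p)/n) with p = 0.0843. For n = 300: √(0.0843 × 0.9157/300) = 1.604%, times 1.96 = 3.14 points, giving 5.29% to 11.57% as printed. The other four rows also reproduce to two decimals. The limits therefore belong to the top three deciles alone.

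**2. Study-population proportion.** P = 0.30 × 8.43% + 0.70 × pL = 2.53% + 0.70 × pL.

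| Assumed pL | P | 8.43% divided by P |
|---|---|---|
| 0% | 2.53% | 3.3 |
| 1% | 3.23% | 2.6 |
| 2% | 3.93% | 2.1 |

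**3. Pooling all rinses without weights does not help.** (300 × 8.43% + 59 × pL)/359 is 25.3/359 = 7.0% at pL = 0% and 26.5/359 = 7.4% at pL = 2%. High-risk patients are heavily over-represented among those tested.

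**4. The decision rule.** P reaches 5.29% only if pL ≥ (5.29 − 2.53)/0.70 = 3.9%. With top-decile positivity at exactly 8.43%, observed results would be:
- 0 of 59 lower-decile positives: 2.5%
- 1 of 59: 2.53% + 0.70 × 1/59 = 3.7%
- 2 of 59: 4.9%
- 3 of 59: 6.1%, the first result above the bound

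The other rows behave the same way. If the high-risk share were 10%, 20%, 40% or 50%, P at pL = 2% would be 2.64%, 3.29%, 4.57% or 5.22% (for example 0.10 × 8.43% + 0.90 × 2% = 2.64%). The printed lower bounds are 2.98%, 4.58%, 5.71% and 5.99%. P is below the bound in every row.

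**5. What the protocol's own count implies.** 300 × 8.43% = 25.3 positives from the top three deciles alone. That already matches the roughly 25 expected from everyone tested, so the planning figures leave almost none for the lower deciles.

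**6. How little the lower stratum can say.** The chance that none of 59 is positive is 0.99^59 = 0.55 at pL = 1% and 0.98^59 = 0.30 at pL = 2%. With 0 of 59 positive, the exact 95% upper limit for pL is 1 − 0.025^(1/59) = 6.1%, which alone would add 0.70 × 6.1% = 4.2 points to P.

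**The case against.** The strongest defence is that section 11.3 describes a model check. The first hypothesis in section 11.1 concerns whether observed positivity matches the model, and top-decile positivity is a sensible quantity for that. If the future study selects patients by the same model, its yield of positives depends mainly on the two quantities section 11.3 names: 30% × 8.43% = 2.5% of those screened. This stands as a reason to keep the check. It does not make the check the primary estimate, and section 11.3 presents it as accomplishing the primary objective.

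A second defence is that section 11 defers further detail to an SAP that is not at hand. Weights and interval methods could be left there. But section 11.3 says positively which outcomes meet the primary objective, and an SAP with a weighted population estimate would depart from that text.

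Four stronger readings are tempting and are not supported:
- **The true proportion is 3% to 4%.** That needs pL between 0.67% and 2.1%, which the protocol does not give. Its count of about 25 positives points nearer 0, and so to about 2.5%.
- **The lower-decile rinses are used nowhere.** The first hypothesis in section 11.1 covers everyone selected for a rinse, and secondary outcome (2) in section 3.2 stratifies by HPV status. The omission is in the primary-analysis text of section 11.3.
- **8.43% will be carried into the 60,000-person study as a population prevalence.** Section 11.3 says only that the pilot will inform point estimates and models for that study.
- **The weighted estimate is good to ±2 to 2.7 points.** Those are normal-approximation half-widths at pL of 1% and 2%. They are unreliable with about one expected positive in 59, and they ignore clustering within about 30 practices.

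Sizing the pilot on risk classification, as section 11.2 does, is a stated choice and not in itself an error.

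**Conclusion.** The point holds. Section 11.3 fixes a primary analysis that does not estimate the outcome defined in sections 3.1 and 3.2, and its decision rule applies top-decile limits to a quantity described as a study-population proportion. The text is wrong as written and needs correcting before the primary analysis.

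For pL of 0% to 2%, the study-population proportion is 2.5% to 3.9%. The expected top-decile positivity overstates it about 2.1 to 3.3 times, and the population figure would normally miss the n = 300 lower bound even if the model were exactly right. The size depends on the assumed pL and on the protocol's planning values of 30% and 8.43%. The mismatch between objective and analysis depends on neither.

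**What to change.** In section 11.3:
- Define the primary estimate as W_high × p_high + W_low × p_low. W is each stratum's observed share of all enrolled patients, and p is the positivity among evaluable rinses in that stratum. Observed shares are safer than fixed weights of 1 and 12, because sections 6.2.1 and 7.2.1 anticipate rinses that cannot be evaluated.
- Give it a confidence interval that remains valid with zero or few positives in the lower stratum, for example one that combines exact stratum limits.
- Report top-three-decile positivity separately as the model check, and reword the decision rule so that the 8.43% limits apply to that quantity only.

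If precision is stated for the primary outcome, in section 11.2 or elsewhere, compute it with the same interval method over a range of pL that starts at 0.

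The cost is revised wording and a small weighted analysis. No new data are needed. The primary estimate will be less precise, because some 70% of the population is represented by about 59 rinses.
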